**9.5 Plans for Data Analysis: To be conducted within each stratum**

1. Tumor Volume: To determine the distributions of volume variables and percent change from baseline. At each scan time point, compute mean, median, range and standard deviation of these variables and plot mean values over time. To compare volume variables at baseline to the values at selected scan time points by paired Wilcoxon signed ranks test.
2. Tumor Motion: At each scan time point, compute mean, median, range and standard deviation of the dose coverage and plot mean values over time. To compare ITV or CTV variables at baseline to the GTV at selected scan time points by paired Wilcoxon signed ranks test.
3. Patient Anatomy: To determine the distribution of patient percent weight loss. At each scan time point, compute mean, median, range and standard deviation of percent weight loss and plot mean values over time.
4. Dose distribution: To determine the distributions of radiation dose to GTV, ITV and critical normal organs. To correlate radiation dose to normal organs with percent weight loss.
5. Conduct exploratory longitudinal analyses to examine changes over time in the 30 patients. Random effects linear regression models will be employed to estimate changes in variables over time clustered by patient. Natural log transformation will be applied prior to modeling.
6. To assess if changes in volume variables are clinically relevant and if so, identify the earliest time point at which re-calibration is warranted. Although it may not be possible to identify a single 're-calibration solution' for all patients in a particular stratum, we will attempt to identify the earliest scan time point at which the majority of patients have clinically important changes in tumor volume or location resulting in over-shoot of the target volume and/or increased dose exposure to normal organs.

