**Primary Aim**

To estimate the degree of tumor volume, tumor motion and patient anatomy change during treatment with photon beam radiotherapy using 4D or 3D CT Scans and/or a serial of MR Imaging.

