### 3.0 SPECIFIC AIMS/OBJECTIVES

**Specific Aim 1:** To estimate the degree of tumor volume, tumor motion and patient anatomy change during treatment with photon beam radiotherapy.

- 1a. To estimate the degree and impact of tumor volume change during the course of definitive photon radiotherapy treatment in lung cancers, head and neck cancers, gastrointestinal cancers (including but not limited to colorectal and rectal cancers) and gynecological cancers.
- 1b. To estimate the degree and impact of tumor motion (anatomic location) change during the course of definitive photon radiotherapy treatment in lung cancers, head and neck cancers, gastrointestinal cancers (including but not limited to colorectal and rectal cancers and gynecological cancers).
- 1c. To estimate the degree and impact of changes in patient anatomy during the course of definitive photon radiotherapy treatment in head and neck and upper gastrointestinal cancers.

Hypothesis: Tumor volume and motion will change over the course of radiation treatment in patients with lung cancers, head and neck cancers, gastrointestinal cancers (including but not limited to colorectal and rectal cancers) and gynecological cancers. The weight loss experienced by patients with upper gastrointestinal and head and neck cancers will have a significant impact on their anatomy. These changes will alter the dose distribution of the photon beam treatment plans, possibly limiting radiation dose delivery to the target volumes and increasing radiation toxicity to surrounding critical structures.

**Specific Aim 2:** To estimate the error if tumor volume, tumor motion and patient anatomy change during treatment with proton beam radiotherapy.

- 2a. To generate simulated proton beam plans using serial CT or MR imaging obtained from either photon or proton beam patients to estimate the dosimetric error if these changes are unaccounted for during proton treatment.

[figure not shown]
Hypothesis: The changes in tumor volume and motion and patient anatomy will have a greater effect on appropriate dose distribution in plans using proton beam therapy compared to photon beam therapy given the need for more accurate target delineation in proton beam therapy.

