### **9.2 *Study Design:***

This pilot study will determine changes over time in tumor volume and motion and patient anatomy, as well as dose distributions to normal organs. The study will inform medical decision-making about the need for (and timing of) re-calibration of radiation dosimetry plans. Up to weekly CT and/or serial MR scans (minimum of 3) will be employed to measure changes in tumor volume and motion and patient anatomy in patients receiving definitive radiation therapy (with or without concurrent chemotherapy). This study is not designed to evaluate the CT or MR procedure. CT or MR is simply the imaging method used for precise measurement of tumor volume variables. Enrollment will be stratified by disease site: NSCLC, Head & Neck, GI and Gynecologic tumors. The study will enroll 30 patients in each stratum. This study is descriptive and not powered hypothesis testing.

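### Section 9.5 items 1 and 2 test for change at unnamed scan time points and specify no confidence interval, although the aim is to estimate how much change occurs

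*Combined protocol and SAP*

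**What the plan says.** The Primary Aim in the Protocol Overview is "To estimate the degree of tumor volume, tumor motion and patient anatomy change during treatment with photon beam radiotherapy", and Specific Aim 1 in section 3.0 repeats it. Section 9.2 adds: "This study is descriptive and not powered hypothesis testing".

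Section 9.5, applied within each disease-site stratum of 30 patients, then plans the following:

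- Item 1, description: "To determine the distributions of volume variables and percent change from baseline", followed by "At each scan time point, compute mean, median, range and standard deviation of these variables and plot mean values over time".
- Item 1, test: "To compare volume variables at baseline to the values at selected scan time points by paired Wilcoxon signed ranks test".
- Item 2, description: the same summaries for dose coverage, which section 9.4 defines as the share of the GTV lying inside the baseline ITV or CTV.
- Item 2, test: "To compare ITV or CTV variables at baseline to the GTV at selected scan time points by paired Wilcoxon signed ranks test".
- Item 4: a correlation of normal-organ dose with weight loss.
- Item 5, labelled exploratory: "Random effects linear regression models will be employed to estimate changes in variables over time clustered by patient", after log transformation.

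The document does not say which time points are selected, or when they will be chosen. It gives no significance level, no rule for multiple tests, no confidence interval and no precision target. Section 9.6 justifies 30 per stratum by patient diversity alone.

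**The concern.** The question is how much change occurs and by when. A signed-rank p-value does not answer it, because it measures only the evidence against zero change. Three things follow.

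1. For tumor volume, zero change is hardly in doubt, so rejecting it tells the reader little.
2. For motion, the test sets two different structures against each other. It can be significant when nothing has moved.
3. Because the time points are not named, they could be chosen after the data are seen. For any variable that may not change, that raises the chance of a spurious significant week.

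At stake is the readability of the result. Section 9.2 expects the study to inform whether and when dosimetry plans are recalculated. A reader needs the size of change at each time, its uncertainty and the number of patients behind it. Section 6.6 allows CT up to weekly and MR with a minimum of 3, at the treating physician's discretion, so the number contributing may differ from week to week.

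**Working it through.** **Inputs.** 30 patients per stratum, four strata (9.2; 4 x 30 = 120, matching the stated total). Four volumes, GTV < ITV < CTV < PTV, measured weekly over 7-8 weeks (9.4). A minimum of 3 MR scans (6.6). The plan states no alpha, power or precision, so there is no error rate or precision figure to reproduce. Two-sided 0.05 is my assumption.

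**1. Is zero volume change a live null?** Section 2.0 cites a median GTV reduction of 44.3% in NSCLC, 69.5% in head and neck cancer, and regression of 69% (radiation alone) or 79% (chemoradiation) in cervical cancer. It gives no volume figure for GI tumors. If all 30 patients shrink, the exact two-sided signed-rank p is 2/2^30 = 1.9 x 10^-9, whether the typical shrinkage is 5% or 70%. The p-value does not carry the size.

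**2. What does the item 2 test detect?** By 9.4, GTV is smaller than ITV, and ITV smaller than CTV. A tumor that neither moves nor shrinks already has a later GTV below its baseline ITV, and shrinkage widens the gap. With every difference in the same direction, p is again 2/2^30 at n=30, and even six patients give 2/2^6 = 0.031. A significant result is therefore not evidence of motion. The dose coverage percentage in the same item bears on motion directly.

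**3. What does free choice of week cost when there is no true change?** With k independent tests, P(at least one p<0.05) = 1 - 0.95^k:

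- k=3: 14.3%
- k=7: 30.2%
- k=8: 33.7%

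Independence is not realistic, because every change is taken from the same baseline scan. If scans are independent with equal variance s^2, two changes have covariance s^2 and variance 2s^2 each, so their correlation is 0.5; patient-specific trends would raise it. I simulated normal changes with mean zero, n=30 and equal correlation between weeks, and counted the runs with any signed-rank p<0.05:

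| Weeks available | Correlation 0.5 | Correlation 0.8 | Independent |
|---|---|---|---|
| 3 | about 12% | about 10% | 14% |
| 7 | about 24% | about 15% | 30% |

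These figures apply to one variable in one stratum.

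**4. What would an interval show?** For a mean change at n=30, the 95% half-width is t(0.975, 29)/sqrt(30) = 2.045/5.477 = 0.373 SD. If the SD of percent change were 10, 20 or 30 points (assumed), that is 3.7, 7.5 or 11.2 points either way. For a median at n=30, the 10th to 21st ordered values give 95.7% coverage. With 20 patients scanned, the half-width for a mean rises to 0.468 SD, which is why the number at each scan should be shown.

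**The case against.** The case on the other side is substantial, and much of it stands.

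- A reader might infer that the Wilcoxon tests are the plan's only inference. They are not: item 5 plans models that estimate change and would yield standard errors, and item 4 plans a correlation.
- A reader might infer that the aim goes unserved, or that no precision is available. Items 1 and 2 require mean, median, range and SD at every scan time point, so the amount and timing of change will be described, and a standard error follows from the SD once n is known. What is missing is a commitment to report n and an interval.
- A reader might infer that only the significant weeks will be reported, or that they will set the re-calibration week. Summaries at all scans limit the first. Item 6 excludes the second: it asks when most patients show clinically important change, and no p-value enters it.
- A reader might multiply 4 volumes by 7-8 weeks by 4 strata and treat 112-128 tests as an error rate. The nested volumes are correlated, most are expected to shrink, and scanning may be less than weekly. The count is a ceiling on possible tests and says nothing reliable about false positives.
- Silence on multiplicity is ordinary in a descriptive pilot, and it does not prove that p-values will go unadjusted.

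Three points survive: the time points are unnamed, no interval is specified, and the item 2 test does not measure motion.

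**Conclusion.** The point holds as a minor one. Items 1 and 2 include tests that do not suit an estimation aim, at time points left open, and no estimate is assigned a confidence interval. The item 2 comparison is the weakest part, because the plan's own definitions make its null false without any motion.

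The selection effect is conditional. If a variable truly did not change, at least one p<0.05 would appear in roughly 10-12% of cases with 3 weeks to choose from and 15-24% with 7, against a nominal 5%. This assumes n=30 at every week, two-sided 0.05 and equal correlation of 0.5 to 0.8. The 30% figure for 7 weeks needs independent weeks and is an upper bound. For tumor volume in lung, head and neck and cervical cancer, the cited reductions make a null of no change implausible, so the issue there is an uninformative p-value more than a false positive. The documents do not support saying that these p-values drive any decision.

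**What to change.** Amend section 9.5 as follows.

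- Item 1: at every scan time point, report the median percent change from baseline with a 95% CI and the number of patients scanned.
- Item 2: at every scan time point, report the median percent of the GTV inside the baseline ITV or CTV, with a 95% CI and the number of patients. Keep the planned range beside it, since this measure cannot exceed 100%. Delete the test of baseline ITV or CTV against later GTV.
- Item 5: report 95% CIs for the modelled changes, back-transformed from the log scale.
- If the item 1 Wilcoxon p-values are kept, give them for all time points and label them exploratory.

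This changes the wording of the analysis plan only. The data and sample size are unaffected, and the cost is longer tables.

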## Quantification of Tumor and Organ at Risk (OAR) Volume and Motion Path Changes during Definitive Photon or Proton Beam Radiotherapy

imaging will be employed as indicated, at the discretion of the treating radiation oncologist. Photon beam treatment plans and Proton beam treatment plans will be generated from these images. Based on the location of the primary tumor, patients will undergo either up to weekly 3D or 4D CT and/or serial MR scans during treatment. These images will be compared to the initial CT/MR scans used for treatment planning and analyzed for changes in tumor volume and tumor anatomic location. At the end of treatment, the frequent 3D or 4D CT and/or serial MR images will be compared to the initial treatment planning images to quantify the changes in tumor volume and tumor motion during the course of radiation treatment. Each CT and/or MR Scan will also be used to evaluate the changes in dose distribution to the target volumes and normal tissues that occur with the initial photon treatment plan and initial proton treatment. The changes in tumor volume, tumor motion and dose distribution during the course of radiation treatment will be analyzed to determine the effect of tumor changes on radiation treatment efficacy.

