## **Quantification of Tumor and Organ at Risk (OAR) Volume and Motion Path Changes during Definitive Photon or Proton Beam Radiotherapy**

expanded to create an internal tumor volume (ITV), which will include the GTV and the extent of GTV respiratory movement as defined by the 4D CT. The clinical tumor volume (CTV) and planning target volume (PTV) will be constructed from the GTV by an automatic margining tool supervised and edited by the treating radiation oncologist. The irradiation target volume will be defined by shaped ports with custom-made blocks or multileaf collimation. Portal verification shall be done for all treated fields. Megavoltage equipment is required with minimum peak photon energies of 6 MV. SAD techniques should be used. Each field will be treated every session. Interruptions in therapy should be discussed with the principal investigator but will be instituted at the discretion of the attending radiation oncologist.

Dose calculation should be performed using inhomogeneity corrections to account for differences in tissue density across the thorax. The total dose to gross disease will be 40-80 Gy, depending on the standard of care for using radiotherapy to treat the primary tumor (with or without concurrent chemotherapy) and on the site of the primary tumor. The prescribed total dose and dose per day will be constrained to adjust for the standard normal tissue dose limitations.

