### **6.6. *On Treatments***

Based on the primary tumor location and the discretion of the treating radiation oncologist, patients will undergo 3D/4D CT Scan (up to weekly) and/or MR Scan (minimum of 3).. The GTV, ITV and critical normal structures will be contoured on each up to weekly/serial scan. The up to weekly/serial GTV volume will be compared to the initial GTV volume to determine changes in tumor volume. Each GTV will be compared to the initial ITV volume to determine what percent of the GTV resides within the initial ITV. This value will be used to evaluate changes in tumor motion. Each ITV will be compared to the initial ITV. The initial photon treatment plan and proton treatment plan will be applied to the new scan. The amount of radiation dose to each GTV, ITV and critical normal structures will be recorded to determine the changes in dose distribution that occur as treatment progresses. **SUBJECTS WILL RECEIVE ALL SCANS IN THE RADIATION ONCOLOGY CLINIC OF THE UNIVERSITY OF PENNSYLVANIA.**

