### **9.3 *Objectives:* To determine changes over time in:**

1. tumor volume variables
2. tumor motion
3. patient anatomy
4. dose distribution to tumor and critical normal organs

**9.4 Endpoints:** To be measured at baseline and then weekly during 7-8 weeks of radiotherapy

1. GTV (gross tumor volume), the volume of the primary tumor visualized on the CT scan
2. ITV (interior tumor volume), the GTV expanded to include interior motion (i.e., breathing or swallowing) such that the tumor resides within the ITV during normal motion
3. CTV (clinical tumor volume), the ITV expanded to include microscopic disease (margins)
4. PTV (planning tumor volume), the CTV expanded by several mm, as determined by radiation dosimetry planning, PTV is considered the ultimate target volume

NOTE the relationship: GTV < ITV < CTV < PTV

5. Dose coverage: at each scan time point, determine the percent of the GTV which resides within the baseline ITV or CTV
5. patient weight and percent weight loss from baseline
6. Radiation dose to critical normal organs based on dose-volume histograms (i.e., 20 Gy to 50% of normal lung tissue)

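### The tumor-motion Wilcoxon test in section 9.5 item 2 does not measure motion: read as volumes it rejects by construction, and read as containment its p-value says little about size

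*Combined protocol and SAP*

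**What the plan says.** Section 9.5 item 2 has two parts. It first summarizes dose coverage at each scan, and then adds a test: "To compare ITV or CTV variables at baseline to the GTV at selected scan time points by paired Wilcoxon signed ranks test".

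Section 9.4 defines GTV, ITV and CTV as volumes, each an expansion of the one before, and states: "NOTE the relationship: GTV < ITV < CTV < PTV". Section 6.5 gives another route to the CTV, which "will be constructed from the GTV by an automatic margining tool", so the CTV exceeds the GTV on that route too. Section 9.4 defines the coverage measure as: "Dose coverage: at each scan time point, determine the percent of the GTV which resides within the baseline ITV or CTV".

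Section 6.6 computes the percent of each GTV lying inside the initial ITV and says: "This value will be used to evaluate changes in tumor motion". It also compares each ITV with the initial ITV, without naming a metric.

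Aim 1b in section 3.0 is: "To estimate the degree and impact of tumor motion (anatomic location) change". Sections 1.0 and 4.0 say the images will be "analyzed for changes in tumor volume and tumor anatomic location". No section defines a distance or direction of displacement.

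**The concern.** Tumor motion is one of three components of the primary aim. The only test listed under it sets one structure at baseline against a different, smaller structure later. By contrast, item 1 of section 9.5 compares each volume variable with its own baseline value.

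A paired test of two quantities that differ by definition can give a very small p-value when nothing has happened. Section 3.0 hypothesizes that tumor volume and motion will change, so such a p-value could be reported as confirmation. Item 6 of section 9.5 also looks for the earliest scan with important changes in tumor volume or location, yet location has no direct measure.

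**Working it through.** **Inputs.** From the documents: 30 patients per stratum (9.2); GTV < ITV < CTV (9.4); cited GTV reductions of 44.3% (lung) and 69.5% (head and neck), and a cited mass displacement of 3.3 mm (2.0). The plan states no alpha, sidedness or effect size for this test, so there is no figure to reproduce. Assumed: two-sided 0.05, spherical tumors, and the radii, margins and noise levels below.

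**1. Volume reading, no noise.** All 30 differences (baseline ITV or CTV minus later GTV) are positive. Exact two-sided p = 2 × 0.5^30 = 1.9e-9, with no motion and no shrinkage.

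**2. Volume reading, with contouring noise.** Radius r = median × exp(0.35 Z). Baseline ITV = (4/3)π(r + m)³ exp(sZ) and later GTV = (4/3)πr³ exp(sZ), with independent Z, n = 30 and 5,000 runs per cell. There is no motion and no volume change. Rejection rates for median radius 15 / 25 / 35 mm:

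| Expansion m | Noise s = 0.10 | Noise s = 0.20 |
|---|---|---|
| 0 mm | 5.1 / 5.2 / 4.9% | 4.4 / 5.2 / 5.2% |
| 1 mm | 99.9 / 93.1 / 71.6% | 82.4 / 44.3 / 24.6% |
| 2 mm | 100 / 100 / 99.6% | 99.9 / 91.7 / 70.7% |
| 3 mm | 100 / 100 / 100% | 100 / 99.7 / 94.1% |
| 5 mm | 100 / 100 / 100% | 100 / 100 / 100% |

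A GTV-to-GTV test under the same null (s = 0.10) rejects in 4.8 / 5.0 / 5.4%. The excess therefore comes from the pairing. It disappears only if the ITV equals the GTV, which the ordering in 9.4 excludes.

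**3. Volume reading, rigid shift.** Moving a body does not change its volume, so p stays at 1.9e-9 for shifts of 0, 3.3, 5, 10 or 20 mm.

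**4. Containment reading.** Baseline is 100% by construction. Ignoring contouring noise, an unmoved and unchanged tumor gives only zero differences and no rejection. Only shortfalls are possible, so with zeros dropped and k patients short, p = 2 × 0.5^k. That is 0.0625 for k = 5 and 0.031 for k = 6, whether each shortfall is 0.1% or 50%.

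**5. What containment registers.** Take a GTV of radius a, a baseline ITV of radius b and a shift d. Containment is 100% when d ≤ b − a. Beyond that the overlap is π(a+b−d)²[d² + 2d(a+b) − 3(a−b)²]/(12d), divided by (4/3)πa³. With a = 20, b = 23 and d = 10 mm: 1089 × 933/120 = 8467, and 8467/10,667 = 79%. The cited reductions multiply the radius by (1 − 0.443)^(1/3) = 0.823 and (1 − 0.695)^(1/3) = 0.673.

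| Margin, shift | No loss | 44.3% loss | 69.5% loss |
|---|---|---|---|
| 3 mm, 10 mm | 79% | 93% | 99.8% |
| 5 mm, 10 mm | 89% | 98.6% | 100% |
| 10 mm, 10 mm | 100% | 100% | 100% |
| 3 mm, 3.3 mm | 99.9% | 100% | 100% |

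Shifts inside the margin do not register. Shrinkage can raise containment for large shifts, but the effect is negligible at the cited 3.3 mm.

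**6. Limits of a centroid measure.** Asymmetric regression alone moves the centroid. For a 20 mm radius, if the residual is a sphere touching the original wall, the movement is 20 × (1 − 0.823) = 3.5 mm or 20 × (1 − 0.673) = 6.5 mm. If tissue is lost on one side of a plane, the residual is a cap of height h with h²(60 − h)/32,000 equal to the remaining fraction. This gives h = 21.5 or 14.7 mm. Its centroid lies 3(40 − h)²/[4(60 − h)] from the original center, which is 6.7 or 10.6 mm.

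With no motion and per-axis registration SD σ, mean vector length is σ√(8/π) = 1.6σ. An assumed σ of 2 mm gives 3.2 mm, close to the cited 3.3 mm.

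**The case against.** The best defense is that the volume reading may not be what was meant. The sentence before the test concerns dose coverage, defined in 9.4 as GTV within the baseline ITV or CTV, and the test repeats that pairing. On the containment reading the test neither rejects for an unmoved tumor nor ignores a shift beyond the margin. Six shortfalls also mean that six tumors left the baseline volume, which is some information, and the summaries in the same item give its size. This stands. A reader might infer that the planned test must reject whatever happens, but the wording does not settle that.

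A reader might also infer that the plan has no measure of motion. It does: section 6.6 names containment for this purpose and also compares each ITV with the initial ITV. Containment is defensible for asking whether the target leaves the planned volume, and the masking example needs an assumed 10 mm shift, about three times the cited displacement. What is absent is a measure of displacement, which the location wording of Aim 1b calls for.

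Finally, section 9.2 calls the study descriptive, no alpha or decision rule uses the test, and section 6.6 provides that "The amount of radiation dose to each GTV, ITV and critical normal structures will be recorded", so the dosimetric effect of a shift is captured elsewhere. This limits the impact but does not make the p-value interpretable.

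**Conclusion.** The concern holds, with low to moderate impact, and should be fixed. On the volume definitions in 9.4, the item 2 test has a false null before treatment starts and cannot respond to a rigid shift. On the containment reading it behaves better, but its p-value reflects how many patients had any shortfall and says little about the amount. Neither reading estimates the degree of motion that Aim 1b asks for.

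The noise-free p-value rests only on the stated ordering and n = 30. The rejection rates rest on assumed spheres, radii, expansions and noise, and fall to 25-82% at 1 mm expansion with 20% noise. Containment remains a valid coverage measure. Its limits are that it does not register shifts inside the margin and that shrinkage can mask large ones.

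**What to change.** In section 9.5 item 2:

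- Delete the Wilcoxon comparison of baseline ITV or CTV with later GTV.
- Keep containment as a descriptive coverage measure with a 95% CI at each scan, and state when the ITV and when the CTV is the reference volume.
- Because Aim 1b treats motion as location, add GTV centroid displacement from baseline after registration (signed per axis, and vector length), shown beside percent GTV change.
- State that vector length is positive even with no motion and should not be tested against zero, and report registration error.
- State that asymmetric regression alone can move the centroid by several mm. For a 20 mm radius sphere this is about 3.5 to 6.7 mm at 44.3% loss and 6.5 to 10.6 mm at 69.5% loss, depending on the assumed shape. These are illustrations, not bounds.

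The cost is SAP wording plus a small amount of registration and centroid calculation from contours already drawn under section 6.6. No new scans or patients are needed.
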